3.8 CONCOMITANT THERAPY

3.8.1 Permitted Concomitant Therapy

Standard supportive care medications are permitted as per institutional standards. These include infectious prophylaxis and symptomatic management, as well as ongoing (begun prior to study enrollment) systemic and topical therapies for acute or chronic GVHD. New topical therapies for cGVHD are also permitted and will not constitute treatment failure.

3.8.2 Prohibited or Restricted Concomitant Therapy

Other investigational agents are prohibited during the course of the study. Additionally, the co-administration of glasdegib and strong CYP3A4 **inducers** is not permitted because this decreases glasdegib levels. While this situation is of less concern in the cGVHD

population than in the acute myeloid leukemia indication, we will follow the FDA-approved guidance regarding CYP3A4 inducers. A list of strong CYP3A4 inducers and inhibitors is provided in Appendix 4.

The potential exists for drug-drug interactions with CYP3A4/5 **inhibitors**, and co-administration of glasdegib in combination with moderate/strong CYP3A4/5 inhibitors is not recommended because this could lead to increased glasdegib levels. Moderate/strong CYP3A4/5 inhibitors (Appendix 4) should be used with caution and only if considered medically necessary. If a moderate/strong CYP3A4/5 inhibitor is to be initiated in addition to glasdegib, please contact the principal investigator for guidance. ECGs should be checked prior to addition of the CYP3A4/5 inhibitor and weekly afterwards x 2 weeks to ensure the QTc interval is < 500 ms. Empiric observations in healthy people and modeling simulation suggest no more than a 12 ms increase in QTc when glasdegib and a CYP3A4/5 inhibitor are combined.

The concomitant administration of glasdegib and drugs with a known risk of Torsades de Pointes (TdP) should be avoided whenever possible because the combination may increase the risk of QTc prolongation. A list of such drugs is provided in Appendix 9. Use of these drugs is not recommended unless there are no alternatives. If a TdP drug is to be initiated in addition to glasdegib, please contact the principal investigator for guidance. ECGs should be checked prior to addition of the TdP drug and weekly afterwards x 2 weeks to ensure the QTc interval is < 500 ms.

3.9 PRECAUTIONS

3.9.1 Pregnancy Prevention

In this study, male subjects who are able to father children and female subjects who are of childbearing potential will receive glasdegib, a compound which has been associated with teratogenic risk. Subjects who are, in the opinion of the investigator, sexually active and at risk for pregnancy with their partner(s) must agree to use at least 1 highly effective form of contraception throughout the study and for at least 30 days after the last dose of investigational product. Male subjects must, additionally, use a condom to prevent potential transmission of investigational product in seminal fluid. The investigator or his or her designee, in consultation with the subject, will confirm that the subject has selected at least 1 appropriate method of contraception from the list of permitted contraception methods (see

Table 2 below) and will confirm that the subject has been instructed in its consistent and correct use. In addition, the investigator or designee will instruct the subject to call immediately if the selected contraception method is discontinued or if pregnancy is known or suspected in the subject or partner.

TABLE 2 Highly effective methods of contraception

Highly effective (failure rate <1 % if used consistently and correctly)	
Low user dependency	High user dependency

• Progestogen-only contraceptive implant• Intrauterine hormone releasing system (IUS)• Intrauterine device (IUD)• Bilateral tubal occlusion• Vasectomized partner	
• Combined hormonal contraception (estrogen and progestogen)
• Oral, intravaginal, transdermal, injectable• Progestogen-only hormonal contraception
• Oral, injectable

3.9.2 Overdose Instructions

Clinical information relevant to overdose is not available. For results from nonclinical overdose studies in rats and dogs, please refer to the Investigator Brochure.

Study drug overdose is the accidental or intentional use of the drug in an amount higher than the dose being studied. An overdose or incorrect administration of study drug is not an AE unless it results in untoward medical effects.

Any study drug overdose or incorrect administration of study drug should be noted on the appropriate CRF.

All Grade ≥ 3 AE's and all SAE's associated with an overdose or incorrect administration of study drug should be recorded.

In the event of subject ingestion of more than the recommended glasdegib dosage, observation for any symptomatic side effects should be instituted, and vital signs, biochemical and hematologic parameters should be followed closely (consistent with the protocol or more frequently, as needed). Appropriate supportive management to mitigate adverse effects should be initiated. If the overdose ingestion of glasdegib is recent and substantial, and if there are no medical contraindications, use of gastric lavage or induction of emesis may be considered.

3.10 DISCONTINUATION OF STUDY TREATMENT

The investigator may discontinue study treatment for any subject, if, in the investigator's opinion, it is not in the subject's best interest to continue. Additionally, a subject has the right to stop study treatment at any time. In addition, subjects may be withdrawn from study treatment for the following reasons:

- Study treatment should be discontinued if the drug is held for a treatment-related toxicity lasting > 28 days as defined above.
- Any subject who starts new systemic immunosuppressive therapy for the treatment of chronic GVHD, becomes pregnant, or is significantly noncompliant should stop study treatment.

The End of Treatment visit should occur 28 days after the last dose of study drug. Patients should be followed on the study schedule, every 3 months (see Section 3.0), unless they start a new systemic immunosuppressive treatment for cGVHD, relapse, or refuse to continue participation. Patients will continue to be followed by chart review for survival, relapse and cGVHD outcomes unless they withdraw consent.

Note that cGVHD progression itself does not require that subjects stop glasdegib unless a new systemic immune-suppressive medication is started. In some circumstances, investigators and subjects may want to continue glasdegib despite documented cGVHD progression if other options are not available.

3.11 REMOVAL FROM STUDY

Reasons for removal of a subject from the study are below. The End of Treatment visit should still be completed approximately 28 days after the last dose, if possible.

- Subject's withdrawal of consent from study
- Decision by sponsor
- Subject lost to follow-up
- Relapse of malignancy
- Death

3.12 DATA AND SAFETY MONITORING

This trial will be monitored in accordance with the Pfizer's Pharmacovigilance procedures. Adverse events, and SAEs will be reviewed internally as part of ongoing safety surveillance.

Monthly communications with the investigators and applicable site staff will be conducted to discuss study progress, obtain investigator feedback and exchange, and discuss "significant safety events" (i.e., AEs leading to dose reductions, related SAEs, and deaths).

In addition, an external DSMB will monitor the study every 6-12 months until the last patient has received 2 months of therapy, unless there are concerns that require ongoing monitoring.

While glasdegib has demonstrated safety, it has not been previously studied in cGVHD therapy after allogeneic hematopoietic cell transplantation. Current evidence suggests that mortality after initiation of cGVHD therapy may be as high as 20% at 56 days in some high-risk patient groups (Blood and Marrow Transplant Clinical Trial Network Protocol 0801). No interim analysis is planned during this trial, but there will be continuous monitoring for a stopping rule if an exact 1-sided 80% confidence interval for the true non-relapse mortality exceeds 10% -- for example, if 2 of first \leq 8, 3 of first \leq 15, 4 of first \leq 20 experience non-relapse mortality in the first 2 months. If the true probability of non-relapse mortality is 5%, the probability of study suspension under the above rule is approximately 0.08; if the true probability is 40%, the probability of suspension is approximately 0.99, estimated from 5,000 simulations, using R version 3.5.0.

Further details of the stopping rule include the following:

- Treatment-related mortality is any death occurring while receiving study drug, or within 30 days after discontinuation of study drug, that is possibly, probably or definitely related to the drug
- Relapse or progressive disease will factor into the attribution of cause but will not automatically prevent a death from being classified as treatment-related
- For purposes of this stopping rule, the count of patients (8, 15, etc) will reflect the order in which patients start treatment
- If a DSMB review is required because the stopping rule is triggered, patients who are already enrolled and taking glasdegib may continue treatment, pending the outcome of that review. Any enrolled patient who has consented but not started study drug may not start glasdegib treatment, pending the outcome of that review.
- The DSMB may, after review, recommend to stop the trial or continue it with or without modifications.

We will also include a stopping rule for grade ≥ 3 AEs that are known to be adverse reactions to glasdegib and hedgehog inhibitor pathway class drugs, such as musculoskeletal pain, muscle spasm, QT prolongation, anorexia, nausea, diarrhea, dizziness, elevated creatinine, elevated

transaminases, and tooth problems. If the lower bound of an 80% exact binomial confidence interval is > 20%, operationally given the total sample size 20, if any 2 of the first 4 or fewer subjects or any 3 of the first 7 or fewer subjects or any 4 of the first 11 or fewer subjects or any 5 of the 15 or fewer subjects or 6 of the first 20 or fewer subjects have unacceptable toxicity or Grade 3 or higher severity AEs, then enrollment will be halted while the DSMB reviews the study. If the true probability of Grade 3 or higher AE is 5%, the probability of study suspension under the above rule is approximately 0.02; if the true probability is 40%, the probability of suspension is approximately 0.85 (probabilities estimated from 5,000 simulations, using R version 3.5.0).

Since 2 of the first 4 patients experienced grade 3 muscle cramping, the stopping rule was triggered. Of note, these 2 patients had cramping prior to enrollment. The DSMB reviewed the data and allowed enrollment to continue but with an exclusion criterion for pre-enrollment grade 2 or 3 muscle cramps, or grade 1 cramps that occur at least weekly. For the purposes of the stopping rule, we will start again with subject #5, so if 2 of the next 4 or fewer, 3 of the next 7 or fewer, 4 of the next 10 or fewer, or 5 of the next 15 have unacceptable toxicity or grade 3 or higher severity AEs, then enrollment will be halted again while the DSMB reviews the study. If the true probability of Grade 3 or higher AE is 5%, the probability of study suspension under the above rule is approximately 0.02; if the true probability is 40%, the probability of suspension is approximately 0.85 (probabilities estimated from 5,000 simulations, using R version 3.5.0).

At the recommendation of the FDA, this trial will include a futility stopping rule for overall response rate by 12 months based on Simon's two-stage design.³⁹ If the null hypothesis is that the true overall response rate (CR+PR) is <20% and the alternative hypothesis is that the response rate is greater than 50%, in the first stage, at least 10 patients will be accrued, and if 2 or fewer responses are observed in the first 10, the study will be suspended. Otherwise, a total of 19-20 patients will be accrued, and the null hypothesis will be rejected if 8 or more responses are observed in 19 patients. This design yields a one-sided type I error rate of 0.025 and power of 80% by minimax. The calculation used R version 3.5.0 and Simon's two-stage design from the following website:

(<http://cancer.unc.edu/biostatistics/program/ivanova/SimonsTwoStageDesign.aspx>). This stopping rule will be evaluated by the DSMB at each meeting but would not be invoked unless the first 10 patients are fully evaluable for overall response rate by 12 months, acknowledging

that that trial may be fully accrued before then. All enrolled and treated patients will be included in this futility analysis.

At the coordinating center at Fred Hutch, the study will be reviewed annually by the Consortium Data and Safety Monitoring Committee (DSMC) according to current Institutional policies. The DSMC will review accrual, unanticipated problems, SAE's, and DSMB reports.

As the Coordinating Center PI and IND holder, the Fred Hutch PI will obtain copies of all local site IRB approvals, will receive and review adverse event reports, and will disseminate that information to the appropriate committees and the DSMB. The Fred Hutch PI will also have responsibility for establishing and carrying out procedures for assessing protocol compliance, data accuracy and completeness, and full and timely reporting of safety data to outside sites.

In addition to continuous safety monitoring by the Investigators, internal monitoring will occur at each site by staff independent of the study team using monitoring plans approved by the National Cancer Institute (since all sites will be Comprehensive Cancer Centers) and reviewed by Fred Hutchinson.

The initial monitoring visit will occur no later than 6 months after the first subject has begun study treatment. Subsequent visits will occur approximately every 6-12 months while subjects are enrolling and receiving study treatment. Monitoring reports will be reviewed by the Fred Hutch PI.

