3.0 STUDY DESIGN

[figure not shown]
This is a single-arm, open-label, phase I/II trial examining the efficacy and safety of glasdegib 50 mg daily for treatment of sclerotic cGVHD. The FDA approved dose is 100 mg of glasdegib daily in the treatment of AML. The MTD in other glasdegib studies in healthy and cancer patients is 400 mg daily.

Twenty subjects will be enrolled. A subject is considered enrolled the day the informed consent form is signed. To control the speed of enrollment and ensure that no more than 20 subjects are enrolled across the study, each participant must be approved by the coordinating center at Fred Hutchinson Cancer Research Center prior to enrollment.

Eligible subjects will undergo up to 24 cycles of study therapy. At this point, there is no study support for longer glasdegib administration or monitoring. If study drug is discontinued prematurely, subjects will still complete remaining study assessments every 3 months through 24 months, unless they refuse continued active participation, relapse, or start a new systemic immunosuppressive treatment, in which case they are followed by chart review only. If subjects discontinue study drug within the first 6 months of study participation (prior to C7D1), they should be seen next at the time point that coincides with an overall every-3-month visit cadence (i.e. C4D1 or C7D1, whichever is next). Any monthly visits in the interim are not required for patients who have stopped glasdegib.

Refer to Appendix 2 for a comprehensive list of study assessments and their timing. The study schema is provided below (FIGURE 1).

Figure 1. Study Schema

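### Section 3.12: the mortality stopping criterion, its list of limits and the stated 0.08 suspension probability do not describe the same rule

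*Combined protocol and SAP*

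**What the plan says.** All of the relevant text is in section 3.12 (Data and Safety Monitoring), apart from the sample size.

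- **Schedule:** "there will be continuous monitoring for a stopping rule".
- **Criterion:** suspension "if an exact 1-sided 80% confidence interval for the true non-relapse mortality exceeds 10" (per cent).
- **Limits:** these are introduced as illustrations, "for example, if 2 of first \leq 8, 3 of first \leq 15, 4 of first \leq 20", where the patients counted "experience non-relapse mortality in the first 2 months".
- **Operating characteristics:** "If the true probability of non-relapse mortality is 5%, the probability of study suspension under the above rule is approximately 0.08", and "if the true probability is 40%, the probability of suspension is approximately 0.99, estimated from 5,000 simulations".
- **Counting:** patients are counted in the order in which they start treatment. The note that says so mentions 8 and 15 as counts.
- **Sample size:** section 3.0 states "Twenty subjects will be enrolled".

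The section sets no minimum number of patients or deaths before the criterion applies, and it does not mention a single death among the first one or two patients.

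**The concern.** A continuously applied confidence-bound criterion fixes its own limits, so the limits and the quoted probabilities can be checked against it. One death in the first patient, or one in the first two, also puts the bound above 10%, yet the list starts at two deaths. Because the list is offered as examples, a reader cannot tell whether the single-death limit was excluded on purpose or simply not mentioned.

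The two rules differ. One halts new treatment starts for DSMB review after a single death in the first two patients; the other does not. The false-suspension probability is the figure by which an IRB, the FDA or the DSMB judges how cautious the rule is, and it should belong to the rule that the text states.

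**Working it through.** **Inputs** (section 3.12 unless noted): one-sided 80% exact bound, so 0.20 in one tail; threshold 10%; a check after every patient; maximum 20 patients (section 3.0); stated suspension probabilities 0.08 at 5% and 0.99 at 40%, from 5,000 simulations.

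**Step 1. Limits implied by the criterion.** The exact (Clopper-Pearson) lower bound for x deaths in n patients is the 0.20 quantile of a Beta(x, n − x + 1) distribution. For x = 1 it reduces to 1 − 0.80^(1/n).

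| Deaths / patients | Lower bound | Above 10%? |
|---|---|---|
| 1 / 1 | 0.200 | yes |
| 1 / 2 | 1 − √0.80 = 0.1056 | yes |
| 1 / 3 | 0.0717 | no |
| 2 / 8 | 0.1044 | yes |
| 2 / 9 | 0.0926 | no |
| 3 / 15 | 0.1041 | yes |
| 3 / 16 | 0.0975 | no |
| 4 / 20 | 0.117 | yes |

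The criterion therefore gives 1 of ≤2, 2 of ≤8, 3 of ≤15 and 4 of ≤20. The last three match the list exactly, which confirms the one-sided reading. The lower limit of a two-sided 80% interval would give 2 of ≤5, 3 of ≤11, 4 of ≤18 and 5 of ≤20, with 0.036 at 5%. That fits neither the list nor the 0.08.

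**Step 2. Reproduce the stated 0.08 with the listed limits.** Deaths only accumulate, so the study escapes suspension if there is at most 1 death by patient 8, at most 2 by patient 15 and at most 3 by patient 20. At 5%:

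- First 8 patients: P(0) = 0.95^8 = 0.6634; P(1) = 8 × 0.05 × 0.95^7 = 0.2793.
- Next 7 patients: P(0) = 0.6983; P(1) = 0.2573; P(2) = 0.0406.
- By patient 15 without a trigger: 0 deaths 0.4633; 1 death 0.3658; 2 deaths 0.0988.
- Last 5 patients: P(≤3) = 1.0000; P(≤2) = 0.9988; P(≤1) = 0.9774.
- No suspension: 0.4633 × 1.0000 + 0.3658 × 0.9988 + 0.0988 × 0.9774 = 0.925.
- Suspension: 1 − 0.925 = **0.075** (0.0748 before rounding).

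The Monte Carlo standard error is √(0.08 × 0.92 / 5000) = 0.0038, so a reported 0.08 is well within simulation error of 0.0748. At 40% the same limits give 0.991, matching the stated 0.99.

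**Step 3. The criterion as worded.** Escape now also needs no death in the first 2 patients, which has probability 0.95² = 0.9025. Given that, repeat the calculation with 6 patients in place of the first 8:

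- Those 6 patients: P(0) = 0.95^6 = 0.7351; P(1) = 6 × 0.05 × 0.95^5 = 0.2321.
- By patient 15 without a trigger: 0 deaths 0.5133; 1 death 0.3512; 2 deaths 0.0896.
- No later suspension: 0.5133 × 1.0000 + 0.3512 × 0.9988 + 0.0896 × 0.9774 = 0.9517.
- Suspension: 1 − 0.9025 × 0.9517 = **0.141**.

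The gap from the stated figure, 0.141 − 0.08 = 0.061, is about 16 Monte Carlo standard errors (0.061 / 0.0038), so simulation noise does not explain it.

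**Step 4. The two rules side by side.**

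| True mortality | Three listed limits | Criterion as worded |
|---|---|---|
| 5% | 0.075 | 0.141 |
| 10% | 0.274 | 0.352 |
| 40% | 0.991 | 0.992 |

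**Step 5. What remains once the first two patients are past.** If neither died within 2 months, both rules have the same limits from then on, and the suspension probability at 5% is 1 − 0.9517 = 0.048 under either.

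**The case against.** The strongest reply is that the three limits are the rule and the confidence bound only explains where they came from. Much of this stands. The quoted probabilities match the listed limits and not the extended set, so the simulation evidently used the list. The counting note names 8 and 15, which also suggests that these are the working checkpoints. A reader might infer from the mismatch that 0.08 was miscalculated; the documents do not support that, because it reproduces for the listed limits.

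A reader might also infer that the trial runs at nearly twice the advertised risk of needless suspension. That does not follow either. The same section reports on the first four patients and restarts the adverse-event count at subject 5, so the two patients to whom the extra limit applies had already started treatment. The section mentions no death among them, and nothing shows that a trigger was missed. A suspension would in any case lead to DSMB review while treated patients may continue, and deaths are discussed in the monthly investigator communications under either reading.

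The reply does not remove the mismatch. If the counts are only examples, 0.08 is not the criterion's figure. If they are the complete rule, the criterion is misstated, because it is also met by one death in two patients. The adverse-event rule in the same section shows the contrast: it presents its limits as the operational form of its criterion, and they are complete. There, one event in one patient gives a bound of exactly 0.20, which does not exceed its 20% threshold.

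**Conclusion.** The point holds as a minor inconsistency between a criterion, its list of limits and its stated operating characteristic. The 0.08 is right for the three listed limits (0.075) and wrong for the criterion as worded (0.141), a difference of 0.066 at a true mortality of 5%. The 0.99 at 40% is right for both. The documents do not settle which version governs.

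The calculation assumes 20 treated patients, independent outcomes with a common probability, and a check after each patient in order of starting treatment. That future conduct is unaffected rests on both of the first two patients having survived their 2-month window without non-relapse death, which is likely but not stated. What remains at stake is the accuracy of the false-suspension figure and of any report on whether the rule was ever met.

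**What to change.** The sponsor should make the criterion, the list and the probability describe one rule. Either of two edits to section 3.12 does this:

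- If the listed limits are the complete rule, replace the words that introduce them as examples with a statement that they are the complete rule, and keep 0.08.
- If the confidence-bound criterion governs, add the limit of 1 death in the first 2 or fewer patients and restate the 5% figure as about 0.14. The 40% figure needs no change.

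Which rule was intended is for the sponsor and the DSMB to state. The cost is one clause, or one added limit and one number. Sample size, data collection and the other limits are unchanged.

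### The mortality stopping rule is set for 2-month non-relapse mortality, but its own details define treatment-related mortality, and nothing reconciles the two

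*Combined protocol and SAP*

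**What the plan says.** Section 3.12 (Data and Safety Monitoring) sets a continuously monitored mortality rule. The trial is suspended if an "exact 1-sided 80% confidence interval for the true non-relapse mortality exceeds 10% -- for example", if 2 of the first 8 or fewer, 3 of the first 15 or fewer, or 4 of the first 20 or fewer patients "experience non-relapse mortality in the first 2 months". For a true non-relapse mortality of 5%, "the probability of study suspension under the above rule is approximately 0.08"; for 40% it is given as about 0.99. Both come from 5,000 simulations.

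A list of further details of the same rule follows. Its first bullet reads "Treatment-related mortality is any death occurring while receiving study drug, or within 30 days after discontinuation of study drug", with the condition "that is possibly, probably or definitely related to the drug". Its second reads "Relapse or progressive disease will factor into the attribution of cause but will not automatically prevent a death from being classified as treatment-related". Its third says that the patient counts (8, 15 and so on) follow the order of treatment start, so the list plainly belongs to this rule.

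On a trigger the DSMB reviews the trial. Patients already on drug may continue, but "Any enrolled patient who has consented but not started study drug may not start glasdegib treatment, pending the outcome of that review". The trigger sentence does not use the term treatment-related mortality, and the document nowhere defines non-relapse mortality.

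**The concern.** The trigger sentence and the bullets describe different events, and neither contains the other. The same death can therefore count under one and not under the other, and with boundaries of 2, 3 and 4 deaths a single reclassified death can decide whether the rule fires.

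The section itself gives reason to expect deaths of disputable cause: it notes that "mortality after initiation of cGVHD therapy may be as high as 20% at 56 days in some high-risk patient groups". That is all-cause mortality in selected groups, not a forecast for this trial. Still, a death of that kind that is non-relapse and not attributed to glasdegib counts only under the trigger sentence.

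At stake is whether and when the formal pause and DSMB review start. Deaths would not go unseen: they are discussed monthly (3.12), every death is a serious adverse event whatever its cause (6.1), and fatal events are reported immediately (6.2). But scheduled DSMB monitoring is only every 6 to 12 months, and those safeguards do not say whether untreated patients are barred from starting drug.

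**Working it through.** **1. The two events side by side (all from 3.12)**

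| Feature | Trigger sentence | Bullets |
|---|---|---|
| Event | Non-relapse mortality | Treatment-related mortality |
| Attribution to drug | Not required | Possibly, probably or definitely related |
| Window | First 2 months | On drug plus 30 days; no 2-month limit stated (treatment lasts up to 24 months, section 3.6) |
| Relapse | Excluded by the term | Not automatically excluded |
| Limit and probabilities | 10%; 0.08 and 0.99 | None stated |

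Three test cases:
- A non-relapse death at week 6, unrelated to drug, counts only under the trigger sentence.
- A drug-related death with relapse counts only under the bullets.
- A drug-related death on treatment at month 9 counts only under the bullets, unless the 2-month limit is carried over.

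**2. The plan's boundaries.** The one-sided 80% Clopper-Pearson lower bound for x deaths in n patients is the 0.20 quantile of a Beta(x, n − x + 1) distribution. It must exceed 0.10.

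| Deaths/patients | Lower bound | Above 0.10? |
|---|---|---|
| 1/1 | 0.200 | yes |
| 1/2 | 0.106 | yes |
| 1/3 | 0.072 | no |
| 2/8 | 0.104 | yes |
| 2/9 | 0.093 | no |
| 3/15 | 0.104 | yes |
| 3/16 | 0.098 | no |
| 4/20 | 0.117 | yes |

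The listed boundaries reproduce. The criterion read literally adds one more: 1 death in the first 1 or 2 patients.

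**3. The plan's suspension probabilities.** An exact binomial recursion over patients 1 to 20 stops when deaths reach 2 by n ≤ 8, 3 by n ≤ 15 or 4 by n ≤ 20.

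| Probability that a patient has the counted event | Listed boundaries | With 1 in the first 1 or 2 added |
|---|---|---|
| 5% | 0.075 (stated 0.08) | 0.141 |
| 10% | 0.274 | – |
| 20% | 0.716 | – |
| 30% | 0.934 | – |
| 40% | 0.991 (stated 0.99) | 0.992 |

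The Monte Carlo standard error of 5,000 simulations near 0.075 is √(0.075 × 0.925 / 5,000) ≈ 0.004. The stated 0.08 therefore fits the listed boundaries and not the literal criterion.

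**4. What the choice of event can do.** The documents give no share of deaths attributed to the drug, so the shares here are assumptions. They illustrate one hybrid reading only: 2-month non-relapse deaths, counted only if judged drug-related. Counted rate = share × non-relapse mortality. At 40%:
- three quarters: 0.75 × 40% = 30%, suspension 0.934
- one half: 0.50 × 40% = 20%, suspension 0.716
- one quarter: 0.25 × 40% = 10%, suspension 0.274

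Without the attribution test it is 0.991. At 20% non-relapse mortality, a share of one half gives a counted rate of 10%, so suspension falls from 0.716 to 0.274.

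Treatment-related mortality as written could also raise the count, through deaths with relapse and deaths after month 2. The documents give no rate for these, so that direction is not quantified.

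**The case against.** The best defence is that the bullets sit under the trigger sentence, so the 2-month window carries over and the bullets only classify deaths. The schedule lends this some support: routine DSMB monitoring runs until the last patient has had 2 months of therapy. Within 2 months, drug-related deaths with relapse should be uncommon, because recurrent or progressive malignancy is an exclusion. That narrows the practical gap on window and relapse. But the reading is inferred, not written, it leaves attribution open, and a bullet that lets deaths with relapse count cannot be squared with a rule on non-relapse mortality.

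The second objection concerns size. The fall from 0.991 to 0.716 takes a 40% rate, twice the highest background figure the section cites, and an assumed share of one half; a test that admits possibly related deaths may give a high share. This is fair. The 40% is used because it is the plan's own design point, and the illustration shows sensitivity, not an expected loss. The net effect is unknown in size and sign.

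Third, a trigger leads to review and not to termination, and deaths are seen anyway. That limits the harm but does not settle when the pause applies.

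**Conclusion.** The inconsistency is real and the rule cannot be applied reproducibly as written. The counted event differs between the trigger sentence and the bullets in attribution, window and relapse, and no text resolves any of the three.

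There is no arithmetic error for the listed boundaries: 0.08 and 0.99 are right, provided the counted event has the stated rate. Whether they describe the rule as it will be run depends on which event is counted. Under the assumed attributed shares of one quarter to three quarters, the probability at 40% would lie between 0.274 and 0.934 instead of 0.991; a shift the other way is possible and cannot be sized from the documents.

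A separate, smaller point: the boundaries are introduced as examples of the confidence-limit criterion. If that criterion is the rule, the figure at 5% is 0.141 and not 0.08.

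**What to change.** Reconcile section 3.12 to one counted event with one window, one attribution rule and one handling of relapse. Define it, and use the same term in the trigger sentence and in the bullets. Which event to count is for the sponsor and the DSMB to decide.

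- If it is non-relapse mortality in the first 2 months, the limit, boundaries and probabilities can stay, provided the text says that the listed boundaries are the rule and not examples.
- If the literal confidence-limit criterion is meant, restate the probabilities for it (0.141 at 5%, 0.992 at 40%).
- If another event is chosen, restate the limit, window and suspension probabilities for that event. If attribution is kept, align its three levels of relatedness with the Yes/No causality item in Appendix 8.

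The cost is wording in one section and at most a short recalculation, with no new data and no extra patients.
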